WALANT Versus Local Anesthesia in Central Venous Catheter Insertion

Unique Protocol Id: B.30.2.ATA.0.01.00/830

Document Date: 01.11.2023

Statistical analyses of the study were performed using the IBM SPSS Statistics for Windows, Version 31.0 (Armonk, NY: IBM Corp) package program. The distributional properties of continuous numerical variables were assessed using visual (histogram and Q–Q plot) and analytical (Shapiro–Wilk test) methods. Comparisons between two independent groups were made for non-normally distributed data using the Mann–Whitney U test, and for normally distributed data using the Independent Samples t-test.

Descriptive statistics for non-normally distributed variables were presented as median, 25%–75% quartiles, and minimum–maximum values, and boxplot plots were used for visual assessment of distribution. Normally distributed data were expressed as mean \pm standard deviation and 95% confidence intervals; error bar graphs were preferred for visual presentation of these variables.

For group comparisons of categorical variables, the Pearson chi-square test or Fisher's exact test was used, depending on the appropriateness of the data. Categorical data were presented as frequency (n) and percentage (%), and were also visualized with bar graphs. In all statistical analyses, a p value of <0.05 was considered statistically significant.

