WALANT Versus Local Anesthesia in Central Venous Catheter Insertion

Unique Protocol Id: B.30.2.ATA.0.01.00/830

Document Date: 01.11.2023

This was a single-center, prospective, observational study conducted between November 1, 2023, and August 1, 2024. Sixty-four adult patients ( $\geq 18$  years) requiring CVC placement were enrolled. Patients were excluded if they were pregnant, had a Glasgow Coma Scale score  $<15$ , were disoriented, had hemorrhagic shock stage  $>1$ , coagulopathy, local infection, or vascular obstruction. Eligible participants were randomized using a single-blind allocation method based on hospital file numbers: odd numbers received WALANT and even numbers received lidocaine. The WALANT solution was prepared according to the standard protocol and injected into a  $3 \times 3$  cm target area 20 minutes before catheter insertion. CVCs were placed without ultrasound guidance in jugular, subclavian, or femoral veins by anatomical localization. Pain intensity was assessed using the Visual Analog Scale (VAS) before and after the procedure.

For the control group, patients requiring CVCs were selected in the emergency resuscitation room and, unless contraindicated, the procedure was performed without any guidance such as ultrasound, after selecting the catheter insertion site (either the femoral vein, subclavian vein, or jugular vein). After marking the anatomical location, the vein to be used was identified by using a 10cc syringe and applying negative pressure to the skin and subcutaneous tissues. While the needle was slowly withdrawn, local anesthesia was induced with an average of 2-10ml lidocaine (1.5-2 mg/kg) applied to the designated  $3 \times 3$  cm area. CVC insertion was then performed according to routine procedures. Patient assessments were recorded using a visual analog scale before and after the procedure.

Data from the case and control groups were statistically analyzed.

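### The SAP names no VAS contrast and gives the pre-procedure VAS no role; baseline-adjusted ANCOVA would be a cheap gain, but only if that score preceded injection in both arms

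*SAP*

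**What the plan says.** **Measurement.** The Protocol's first paragraph states "Pain intensity was assessed using the Visual Analog Scale (VAS) before and after the procedure". Its second paragraph says the same for the control group: "Patient assessments were recorded using a visual analog scale before and after the procedure". Neither sentence places the first score relative to the anesthetic injection.

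**Injection timing.** WALANT went into a "cm target area 20 minutes before catheter insertion". For controls, "While the needle was slowly withdrawn, local anesthesia was induced with an average of 2-10ml lidocaine", after the vein had been located and before the catheter was inserted.

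**Analysis.** The SAP's first paragraph gives "Comparisons between two independent groups were made for non-normally distributed data using the Mann–Whitney U test", and the independent-samples t-test for normally distributed data. Its third paragraph adds Pearson chi-square or Fisher's exact test for categorical data and closes with "In all statistical analyses, a p value of <0.05 was considered statistically significant". The SAP lists no adjusted, paired or repeated-measures method. It does not mention VAS and names no primary contrast.

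**Size and allocation.** "Sixty-four adult patients" were enrolled, allocated by file number: "odd numbers received WALANT and even numbers received lidocaine". Neither document gives arm sizes, an effect size, a VAS standard deviation or a before–after correlation.

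**The concern.** A pain score taken before treatment usually predicts the score taken after it. When such a score is already on file, adjusting for it removes the variance it explains, with no new data. With 64 patients that could matter, and the SAP says nothing about doing so.

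Because no outcome variable is named, the listed tests could be run on the post-procedure score, on the change, or on each time point. These have different precision, and they react differently if the first score is not a true baseline.

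The timing raises that doubt. If the procedure is taken to begin when the operator starts, the WALANT score could follow its injection while the control score precedes lidocaine. If it means catheter insertion alone, both scores could follow injection. If it includes the injection, both precede it. The Protocol supports no one reading over the others. Adjusting for, or subtracting, a score already affected by treatment removes part of the treatment effect or creates a false one.

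**Working it through.** The plan contains no power calculation to reproduce.

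**Inputs.** From the documents: 64 patients and alpha 0.05. Assumed: 32 per arm, two-sided test, normal data, a true effect of 0.5 SD of the post-procedure score, and correlation ρ from 0 to 0.7.

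**1. Unadjusted post-procedure score.** Noncentrality = 0.5 × √(32/2) = 2.0 on 62 df. Power is 50.4%.

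**2. ANCOVA.** The variance is multiplied by (1 − ρ²) × (1 + 1/60); the second factor is the average cost of chance covariate imbalance. Noncentrality = 2.0/√[(1 − ρ²)(61/60)] on 61 df. At ρ = 0.5 the factor is 0.75 × 1.0167 = 0.7625, the noncentrality 2.29 and the power 61.6%.

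| ρ | Power, with imbalance cost | Power, without it | CI width factor √(1 − ρ²) |
|---|---|---|---|
| 0 | 49.7% | 50.3% | 1.00 |
| 0.1 | 50.1% | 50.7% | 0.995 |
| 0.3 | 53.5% | 54.1% | 0.954 |
| 0.5 | 61.6% | 62.3% | 0.866 |
| 0.7 | 78.0% | 78.7% | 0.714 |

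Break-even is where (1 − ρ²)(61/60) = 1, so ρ = √(1/61) = 0.13. The loss at ρ = 0 is 50.4 − 49.7 = 0.7 points. Unequal arms change little: with a 24/40 split and without the imbalance cost, power is 48% unadjusted against 60% at ρ = 0.5 and 76% at 0.7.

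**3. Bounded, rounded 0–10 scores.** Two assumed settings were simulated, one with a floor effect, comparing Mann–Whitney with ANCOVA using HC3 standard errors.

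| ρ | Mann–Whitney | ANCOVA, HC3 | Difference (points) |
|---|---|---|---|
| 0 | 46.7–47.7% | 44.1–46.6% | −1 to −3 |
| 0.3 | 46.2–47.9% | 46.5–50.5% | 0 to +3 |
| 0.5 | 45.8–47.8% | 53.8–57.2% | +8 to +9 |
| 0.7 | 45.7–48.6% | 68.5–74.3% | +23 to +26 |

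Under the null, HC3 rejection stayed at 4.2–4.8%.

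**4. Change score.** With k = SD before / SD after, its variance relative to the post score is 1 + k² − 2ρk. At k = 1 and ρ = 0.3 this is 1.4 and power is 38%, below the 50% of the post score alone. At k = 2, power is 14–26% over the whole range of ρ.

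**5. Pre-procedure score taken after injection in the WALANT arm only.** Suppose the injection lowers that score by δ SD and the lowering does not carry into the post score. The ANCOVA estimate then shifts by ρδ. With δ = 0.5 and no true effect:

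| ρ | Shift ρδ | Standard error | Type I error, formula | Type I error, simulated |
|---|---|---|---|---|
| 0.3 | 0.15 | 0.248 | 9.1% | 9.4% |
| 0.5 | 0.25 | 0.225 | 19.4% | 19.7% |
| 0.7 | 0.35 | 0.186 | 45.8% | 45.7% |

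The standard error is √[(1 − ρ²)(2/32 + (δ² + 2/32)/60)]. With δ = 0.3 the simulated rates are about 7 / 10 / 20%. A true 0.5 SD reduction is estimated as 0.5 − ρδ, or 0.35 / 0.25 / 0.15 SD at δ = 0.5. The change score estimates 0.5 − δ, which is zero at δ = 0.5. The unadjusted post score is not affected by this shift.

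**The case against.** **The gain is unknown and may be nil.** This stands. The documents give no correlation, and at 0.3 or below the gain is nil to about 3 points. With an early WALANT injection and patients in different degrees of pain at the start, the correlation could be anything in the range shown.

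**The gain is largest where a timing mistake does most harm.** This also stands. Both grow with ρ, so the advice is only as good as the timing check.

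**A linear model changes what is compared.** True: an adjusted mean difference replaces the Mann–Whitney comparison of distributions, and the report should say so.

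**The analysis may be too late to pre-specify.** Both documents are written in the past tense and enrollment is described as ending on August 1, 2024. If results are known, ANCOVA can only be a labeled post hoc analysis.

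A reader might also infer that the SAP discards the pre-procedure score. The text does not support that: it names no variable, so the listed tests could be applied to that score or to the change. What can be said is that it states no role for it.

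**Conclusion.** The point holds as a low-cost improvement in precision and clarity, conditional on timing. Under the stated assumptions, gains become material from a correlation of about 0.3–0.5: about 12 points of power at 0.5 and 28 at 0.7 with normal data, less on a bounded scale. The cost at zero correlation is 0.7 points, or 1–3 with HC3 errors. Naming a single VAS contrast is worthwhile whatever the correlation.

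Four stronger readings go beyond the documents:

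- **That the unadjusted test is an error.** Leaving out a baseline covariate does not bias a comparison of the arms. Whether the arms are comparable under file-number allocation is a separate question, and neither analysis settles it.
- **That ANCOVA is free.** It has the small costs above, and a large one if the timing is wrong.
- **That the WALANT score was taken after injection.** This is one of three readings. The 0.5 SD shift is an assumption that shows the hazard, not an estimate.
- **That the error rate is already inflated by testing both post and change scores.** If both were tested and either could be claimed, simulated false-positive rates run from about 7% to 10% for SD ratios of 0.5 to 2. Nothing in the documents shows that this was done.

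**What to change.** 1. Confirm from study records when the pre-procedure VAS was taken in each arm relative to the anesthetic injection, and state it in the Protocol.
2. If it preceded any injection in both arms, make the single primary contrast post-procedure VAS by ANCOVA with arm and pre-procedure VAS. Report the adjusted mean difference, its 95% CI and a robust or permutation p-value.
3. If it did not, or if the records cannot show it, make unadjusted post-procedure VAS the single primary contrast.
4. In either case treat change scores as descriptive.
5. If results are already known, label the ANCOVA as not pre-specified and report the unadjusted result alongside.
6. Do not present adjustment as a remedy for possible selection through file-number allocation.

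The cost is a check of study records, one linear model on data already collected, and a few lines of SAP text. No new data are needed. If results are known, rewording cannot restore pre-specification; only disclosure is possible.

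### The SAP calls p<0.05 significant in every analysis and names no primary VAS comparison; if the after score and the change can each support a pain claim, the false-positive rate is about 8-10%, not 5%.

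*SAP*

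**What the plan says.** The last paragraph of the SAP sets one threshold for everything: "In all statistical analyses, a p value of <0.05 was considered statistically significant". For two-group comparisons the SAP assigns a test by distribution: "Comparisons between two independent groups were made for non-normally distributed data using the Mann–Whitney U test", with the independent-samples t-test when the data look normal. Categorical variables get a chi-square or Fisher test. It lists no paired, change-score or baseline-adjusted analysis.

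The Protocol's first paragraph gives two pain scores per patient: "Pain intensity was assessed using the Visual Analog Scale (VAS) before and after the procedure". The control-group paragraph says the same: "Patient assessments were recorded using a visual analog scale before and after the procedure". The Protocol's whole statement on analysis is "Data from the case and control groups were statistically analyzed". No primary outcome, time point, contrast or multiplicity rule appears in either document.

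The before score is not placed relative to the anaesthetic. WALANT goes into the "target area 20 minutes before catheter insertion". In the control arm, lidocaine is injected as the locating needle is withdrawn. Neither paragraph says whether the before score came ahead of the injection.

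**The concern.** One scale measured twice does not give one test. The arms can be compared on the after score, on the change, or on the before score, and the SAP's two-sample tests can be run on each. The SAP accepts p<0.05 from any of them and does not say which one decides whether WALANT changes pain.

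If the claim can rest on whichever comparison crosses 0.05, the reported p value understates the risk that the claim is false. A reader of the results could not tell a planned finding from the best of several. This bears on the only outcome measure the documents name.

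**Working it through.** **Inputs from the documents**
- Threshold of 0.05 for each test (SAP, last paragraph).
- Two VAS time points (Protocol, first paragraph and control-group paragraph).
- Sample size: "Sixty-four adult patients".
- Allocation by file number: "odd numbers received WALANT and even numbers received lidocaine".

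**Assumptions, because the documents give no value**
- Tests are two-sided, so the critical value is 1.96.
- The correlation ρ between before and after scores is anywhere from 0 to 0.9.
- The two scores have equal variance.
- Arms are 32 and 32 in the simulation.
- There is no true difference between arms on any VAS score.

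The plan gives no family-wise rate, power or sample-size calculation, so there is no stated figure to reproduce first. The 0.05 is a declared threshold.

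**Step 1: benchmark with independent tests.** The chance of at least one p<0.05 in k tests is 1 − 0.95^k: 5.0% for k=1, 9.75% for k=2, 14.3% for k=3.

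**Step 2: correlated VAS contrasts.** The before and after test statistics have correlation ρ. The after score and the change have correlation √((1−ρ)/2). For two contrasts, P(either significant) = 0.05 + 0.05 − P(both significant), with the joint term from the bivariate normal distribution. For example, at ρ=0.5 the after/change correlation is √0.25 = 0.5, P(both) = 0.0093, and the rate is 0.10 − 0.0093 = 9.07%. Rates for three contrasts come from 4,000,000 simulated draws.

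| ρ | before or after | after or change | after, change or ANCOVA | before, after or change |
|---|---|---|---|---|
| 0 | 9.75% | 8.31% | 8.30% | 11.49% |
| 0.3 | 9.51% | 8.78% | 9.15% | 12.08% |
| 0.5 | 9.07% | 9.07% | 9.66% | 12.20% |
| 0.7 | 8.35% | 9.35% | 10.07% | 12.04% |
| 0.9 | 7.04% | 9.62% | 10.25% | 11.32% |

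Counting all four contrasts (before, after, change, ANCOVA) gives 11.5-12.8% over the same range.

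**Step 3: the SAP's own test rule.** The rule (Shapiro-Wilk, then t-test or Mann-Whitney) was simulated with 32 per arm, normal data and rounded 0-10 VAS data, ρ of 0.3, 0.5 and 0.7, and 6,000 runs per setting:
- one contrast: 4.8-5.9%;
- after or change: 8.9-10.0%;
- before or after: 8.1-9.7%;
- before, after or change: 11.9-13.4%.

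The simulation error on a 5% rate is √(0.05×0.95/6000), about 0.3 percentage points. The 13.4% comes from the setting in which two of the single-test rates also ran high (5.9% and 5.8%), so it sits a little above the 12.2% in the table partly by chance.

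**Step 4: after the fix.** One pre-specified comparison at two-sided 0.05 has a rate of 5.0%. If more than one is kept, Bonferroni gives 0.05/2 = 0.025 each for two, or 0.05/3 = 0.0167 each for three, and holds the family at or below 5%.

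**The case against.** The strongest reply is that the SAP sentence is an ordinary per-test threshold. It does not say that any significant VAS contrast proves an effect, and the documents never mention a change score. If only the after score was compared, the error rate is 5% and nothing is inflated. That stands, and it is why the figures here are conditional. What survives is that nothing in either document commits the study to a single comparison, so the threshold as written does not protect the pain claim.

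Three stronger readings are tempting and are not supported.

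- *The documents fix the error rate at 9-13%.* They do not. They are compatible with anything from 5% to about 13%, depending on how many contrasts are tested and how the result is read. Two time points alone give about 7-10%.
- *A difference in the before score would count as evidence about WALANT.* If that score precedes the injection, a difference is baseline imbalance and cannot support such a claim. The 12-13% figure matters only if the before score could follow the injection, or would be read as evidence anyway. The Protocol leaves the timing open.
- *The option of t-test or Mann-Whitney adds further inflation.* The SAP assigns the test by distribution. The plots leave some judgement, but reporting whichever p value is smaller is not the written rule.

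A further objection concerns timing. Both documents are dated 01.11.2023 yet describe, in the past tense, a study that ran to August 2024. A reader might infer that the plan was written after the data were seen. The documents do not settle this, but if it were so, naming a primary comparison now would not restore 5%.

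**Conclusion.** The concern holds in conditional form. The SAP treats p<0.05 as significant everywhere and does not single out a VAS comparison. The false-positive rate for a pain claim is then:

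- 5% if one contrast is tested;
- about 8-10% if the after score and the change can each carry the claim;
- up to about 12-13% only if the before score is also counted.

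At ρ=0.5 the middle case is 9.07%, about 1 in 11 rather than 1 in 20. The sizes rest on the assumptions listed in the working, and the direction does not depend on ρ within the range examined. The point should be corrected because it affects the only named outcome measure and costs little to settle. Allocation by odd and even file number is a separate source of bias that no change to the significance rule addresses.

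**What to change.** Replace the last sentence of the SAP with text along these lines: *The primary comparison is post-procedure VAS between arms, estimated by a linear model (ANCOVA) adjusted for pre-procedure VAS and tested once at two-sided 0.05. All other comparisons are secondary and are reported with estimates and 95% confidence intervals.* Say also that this model is used regardless of the normality check, so that it does not conflict with the SAP's rule for choosing between the t-test and Mann-Whitney.

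Two statements must accompany it:

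1. **Timing of the before score.** State whether it was taken before the anaesthetic injection in both arms. If it was not, it may already reflect treatment, and adjusting for it could remove or distort the effect. In that case make unadjusted post-procedure VAS the single primary comparison.
2. **Timing of the choice.** If the data had already been seen, say when the primary comparison was chosen and report all VAS contrasts. Alternatively, apply Bonferroni across every contrast tested (0.025 each for two, 0.0167 each for three).

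The cost is a few sentences and one model. No new data are needed, because both scores are already collected. The small downside is that secondary comparisons no longer support a confirmatory claim.
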